| Duration of Study: | Patients who receive one treatment cycle will be in this study for up to approximately 8 weeks: up to a 28-day Screening period, a 21-day Treatment cycle, and a Follow-up period out to 28 ± 5 -days after the last dose (i.e., approximately Day 33). After the first treatment cycle, patients may continue to receive cycles of CPX-POM until progression of disease, intolerable toxicity occurs, or another withdrawal criterion applies. |

| | |
|---|---|
| Diagnosis and Main Eligibility Criteria: | 
Patients eligible for enrollment in this study will be adults with any histologically- or cytologically-confirmed metastatic or advanced-stage solid tumor that is refractory to standard therapy. Patients should only be included if no therapy exists or if they have received all standard therapies that would be potentially curative or might provide significant benefit. Patients must have a life expectancy ≥ 3 months, an Eastern Cooperative Oncology Group (ECOG) Performance Status 0 or 1, no significant ischemic heart disease, adequate hepatic function, and a baseline glomerular filtration rate (GFR) > 50 mL/min/1.73m². Females must not be pregnant and, if of childbearing potential, must use an effective method of contraception to avoid pregnancy during and for 3 months after participation in the trial.
 
Patients who have any risk factor for torsade de pointes or any uncontrolled or severe intercurrent medical condition, or who have had major surgery or prior systemic chemotherapy or radiation therapy within the previous 4 weeks are excluded.
 |
| Test Product, Dose, and Mode of Administration: | 
Escalating doses of CPX-POM will be administered by 10-minute IV infusion once daily on Days 1-5 of each 21-day cycle.
 
After completion of Cycle 1 for the first 4 to 6 patients, the SRC will review safety, PK, and PD data to determine if any changes to the dosing schedule are indicated (e.g., adding an additional 5 days of dosing to each treatment cycle).
 
Patients may continue to receive cycles of CPX-POM until progression of disease, intolerable toxicity occurs, or another withdrawal criterion applies. The starting dose will be 30 mg/m².
 |
| Reference Therapy, Dose, and Mode of Administration: | 
Not applicable.
 |

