7. Pregnancy tests will be required only for women of child bearing potential at Screening and before dosing on Day 1 of each treatment cycle. Urine or serum pregnancy tests are acceptable.
8. Cancer evaluation will include determination of staging and metastases for screening purposes (see Section 8.1). Disease response assessments will be performed for patients with measurable disease within 28 days prior to the first dose of CPX-POM and repeated at the end of every second cycle (i.e., at approximately 6-week intervals). During the Dose-Escalation Phase of the study, Screening cancer evaluations may be performed up to 28 days before Cycle 1, Day 1. For patients enrolled in any Expansion cohorts, Screening cancer evaluations must be performed within 28 days of Cycle 1, Day 1.
9. Hematology will include measurement of hemoglobin, hematocrit, platelets, RBC, reticulocytes, and WBC with differential. To shorten the duration of the Cycle 1, Day 1 visit, if needed, the safety laboratory blood samples required for this visit may be drawn up to 3 days before Day 1 (Cycle 1 only).
10. Clinical chemistry will include measurement of potassium, sodium, chloride, glucose, BUN, creatinine, creatinine clearance, ALT, AST, ALP, GGT, alkaline phosphatase, indirect bilirubin, direct bilirubin, total bilirubin, total protein, albumin, calcium, bicarbonate, magnesium, phosphate, lipase, and amylase. To shorten the duration of the Cycle 1, Day 1 visit, if needed, the safety laboratory blood samples required for this visit may be drawn up to 3 days before Day 1.
11. Thyroid panel will include TSH, free T4, and free and total T3 and will be repeated on D1 of each cycle.
12. Coagulation tests will include PT and aPTT and will be repeated on D1 of each cycle.
13. Urinalysis will include color, turbidity, pH, specific gravity, glucose, ketones, nitrites, bilirubin, urobilirubin, protein, RBCs, WBCs, epithelial cells, casts, crystals, and bacteria, and eGFR at Screening only.
14. A full physical examination will be conducted at Screening and at Follow-up. At each other study visit, patients will be assessed for continued dosing and any possible physical symptoms/toxicities and a physical examination may be performed, if indicated. Body weight should be measured at each study visit. Height should be measured at Screening.

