Approximately 24 patients will be enrolled in the Single-Patient and Standard Dose Escalation Cohorts to establish the MTD. In addition to these estimated 24 patients, Expansion Cohort(s) may be enrolled after the MTD is reached to either explore different dosing schedules, increase the experience with a particular tumor type (e.g., muscle invasive

bladder cancer [MIBC]), or to examine the safety and anti-tumor activity of CPX-POM in combination with certain other anticancer agents.

All patients are to attend a Follow-up Visit 28 days (\pm 5 days) after the last study drug dose. No follow-up after completion of the Follow-up Visit is planned, with the exception of monitoring of ongoing treatment-emergent adverse events (AEs) until resolution or until the AE is clearly determined to be due to a patient's stable or chronic condition or intercurrent illness(es).

Dose escalation procedures will be conducted as shown in Table 2. For further details and example doses, see Section 4.2.

Table 2. Dose Escalation Procedures

| Accelerated Titration (Single-Patient Cohorts; n=1 each) | |
|---|---|
| No \geq Grade 2 AEs | 
 Continue evaluation of single-patient dose cohorts. Escalate by 100% to next dose level. |
| At least 1 \geq Grade 2 AE not meeting the definition of DLT | 
 Expand current and subsequent cohorts to at least 3 patients (see Standard Dose Escalation Scheme below). |
| 1 DLT | 
 Expand current cohort up to 6 patients or until 2 DLTs are encountered (Standard Dose Escalation Scheme below). |
| Standard Dose Escalation (Standard Cohorts; n=3 to 6 each) | |
| No DLT | 
 Escalate by 25–50% to next dose level. |
| 1 DLT in \leq 3 patients | 
 Expand cohort up to 6 patients. |
| 1 DLT in 6 patients | 
 Escalate by 25–50% to next dose level. |
| > 1 DLT in \leq 6 patients | 
 MTD reached; stop dose escalation. Possibly explore intermediate doses for the RP2D. |

Abbreviations: AE = adverse event; DLT = dose limiting toxicity; MTD = maximum tolerated dose; RP2D = recommended Phase 2 dose.

A Dose-Limiting Toxicity will be defined as any of the following, if deemed related to study drug:

- Grade 4 thrombocytopenia of any duration
- Grade 3 thrombocytopenia with significant hemorrhage of any duration

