7.2. Patient Discontinuation/Withdrawal from the Study

A patient may withdraw from the study at any time at his/her own request, or may be withdrawn at any time at the discretion of the investigator for safety, behavioral, compliance, or administrative reasons.

If the patient withdraws consent for disclosure of future information, the Sponsor may retain and continue to use any data collected before such a withdrawal of consent.

If a patient withdraws from the study, he/she may request destruction of any samples taken and not tested, and the investigator must document this in the site study records.

If a patient withdraws prematurely from the trial for any reason, study staff should make every effort to complete the full set of evaluations scheduled for the Follow-up/Early Termination visit. See the Schedule of Assessments (Table 1) for data to be collected at the time of early termination.

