8. STUDY ASSESSMENTS

8.1. Cancer Evaluation

All patients will undergo a cancer evaluation to include determination of staging and metastases for screening purposes. Disease response assessments will be performed for patients with measurable disease within 28 days prior to the first dose of CPX-POM and repeated before the first study drug dose (Day 1) of every second cycle (i.e., at approximately 6-week intervals). If a patient with measurable disease discontinues from the study after 6 weeks and before a disease response assessment is scheduled, an additional assessment may be performed, upon consultation with the Sponsor, at the end of treatment (i.e., on approximately Day 22 of the last cycle).

For the screening assessments, all sites of disease will be imaged by CT, if possible. If the anatomic region cannot be adequately imaged by CT, magnetic resonance imaging (MRI) may be used instead. Subsequent assessments should use the same radiographic methods as used during Screening. Disease response will be assessed by the investigator using RECIST, version 1.1 (Eisenhauer et al, 2009; see Appendix 1). Tumor markers applicable to the patient's solid tumor type (e.g., prostate-specific antigen [PSA] for prostate cancer; cancer antigen-125 [CA-125] in ovarian cancer; carcinoembryonic antigen [CEA] in colorectal or pancreatic cancer, cancer antigen 19-9 [CA-19-9] in pancreatic cancer) will also be measured within ± 2 days of tumor measurements.

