PK Population	XX (XX.X)	XX (XX.X)	XX (XX.X)	XX (XX.X)	XX (XX.X)	XX (XX.X)	XX (XX.X)

Percentages are based on the number of enrolled patients.

The Safety population includes all patients who have received at least one dose of CPX-POM.

The Efficacy population includes all patients who have received at least one dose of CPX-POM, had RECIST measurable disease at baseline and had at least one other post-baseline tumor assessment.

The PK population includes all patients for whom at least one plasma and/or urine sample has been obtained and analyzed for determination of plasma drug and metabolites concentration.

Program: (Program name.sas) (run on: DDMMYYYY HH:MM)

Filename: (Specify file name.rtf)

PROGRAMMING NOTES:

- For the safety population, patients are displayed based on the actually received treatment.

Sponsor: CicloMed
Protocol: CPX-POM-001
Statistical Analysis Plan
(TFL shells):
Version 1.0 / 02FEB2018

Protocol: CPX-POM-001

--- DELIVERY TYPE ---

Page 1 of 3

Table 14.1-3 - Summary of Demography
 (ITT Population)

	CPX-POM 30 mg/m ² N=1	CPX-POM [D2] mg/m ² N=X	CPX-POM [D3] mg/m ² N=X	CPX-POM [D4] mg/m ² N=X	CPX-POM [D5] mg/m ² N=X	CPX-POM [D6] mg/m ² N=X	CPX-POM [D7] mg/m ² N=X
Age [a] (years)							
n	XX	XX	XX	XX	XX	XX	XX
Mean	XX.X	XX.X	XX.X	XX.X	XX.X	XX.X	XX.X
SD	XX.XX	XX.XX	XX.XX	XX.XX	XX.XX	XX.XX	XX.XX
Minimum	XX	XX	XX	XX	XX	XX	XX
Median	XX.X	XX.X	XX.X	XX.X	XX.X	XX.X	XX.X
Maximum	XX	XX	XX	XX	XX	XX	XX
Age group [n (%)]							
< 65 years	XX (XX.X)	XX (XX.X)	XX (XX.X)	XX (XX.X)	XX (XX.X)	XX (XX.X)	XX (XX.X)
≥ 65 years	XX (XX.X)	XX (XX.X)	XX (XX.X)	XX (XX.X)	XX (XX.X)	XX (XX.X)	XX (XX.X)
Sex [n (%)]							
Male	XX (XX.X)	XX (XX.X)	XX (XX.X)	XX (XX.X)	XX (XX.X)	XX (XX.X)	XX (XX.X)
Female	XX (XX.X)	XX (XX.X)	XX (XX.X)	XX (XX.X)	XX (XX.X)	XX (XX.X)	XX (XX.X)
Race [n (%)]							
White	XX (XX.X)	XX (XX.X)	XX (XX.X)	XX (XX.X)	XX (XX.X)	XX (XX.X)	XX (XX.X)
Black or African American	XX (XX.X)	XX (XX.X)	XX (XX.X)	XX (XX.X)	XX (XX.X)	XX (XX.X)	XX (XX.X)
Asian	XX (XX.X)	XX (XX.X)	XX (XX.X)	XX (XX.X)	XX (XX.X)	XX (XX.X)	XX (XX.X)
American Indian or Alaska Native	XX (XX.X)	XX (XX.X)	XX (XX.X)	XX (XX.X)	XX (XX.X)	XX (XX.X)	XX (XX.X)
Native Hawaiian or Other Pacific Islander	XX (XX.X)	XX (XX.X)	XX (XX.X)	XX (XX.X)	XX (XX.X)	XX (XX.X)	XX (XX.X)
Other	XX (XX.X)	XX (XX.X)	XX (XX.X)	XX (XX.X)	XX (XX.X)	XX (XX.X)	XX (XX.X)

[a] Age at Screening.

[b] Body mass index (BMI) (kg/m²) = Weight (kg) / (Height (m))².

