Table 14.1-6.1.2 - Concomitant Medications by Therapeutic Class and Preferred Term
(Safety Population)

Replicate of Table 14.1-6.1.1

PROGRAMMING NOTES:

- Update footnote: replace 'A prior medication is a medication whose end date is before the date of first CPX-POM dose' by 'A concomitant medication is a medication that started before the date of first dose and stopped on (or is ongoing after) the date of first dose OR a medication whose start date is either the same as (or after) the date of first dose'.
- Update 'At least one prior medication' by 'At least one concomitant medication'.
- The Therapeutic Classes are presented by alphabetical order and the Preferred Terms are sorted within Therapeutic Classes by alphabetical order.
- A medication / therapy can appear within more than one Therapeutic Class.

Table 14.1-7 - Overall Exposure to Study Drug and Drug Compliance
 (Safety Population)

	CPX-POM 30 mg/m ² N=1	CPX-POM [D2] mg/m ² N=X	CPX-POM [D3] mg/m ² N=X	CPX-POM [D4] mg/m ² N=X	CPX-POM [D5] mg/m ² N=X	CPX-POM [D6] mg/m ² N=X	CPX-POM [D7] mg/m ² N=X
Study Drug Exposure (days) [a]							
n	XX	XX	XX	XX	XX	XX	XX
Mean	XX.X	XX.X	XX.X	XX.X	XX.X	XX.X	XX.X
SD	XX.XX	XX.XX	XX.XX	XX.XX	XX.XX	XX.XX	XX.XX
Minimum	XX	XX	XX	XX	XX	XX	XX
Median	XX.X	XX.X	XX.X	XX.X	XX.X	XX.X	XX.X
Maximum	XX	XX	XX	XX	XX	XX	XX
Study Drug Exposure (mg) [b]							
n	XX	XX	XX	XX	XX	XX	XX
Mean	XX.X	XX.X	XX.X	XX.X	XX.X	XX.X	XX.X
SD	XX.XX	XX.XX	XX.XX	XX.XX	XX.XX	XX.XX	XX.XX
Minimum	XX	XX	XX	XX	XX	XX	XX
Median	XX.X	XX.X	XX.X	XX.X	XX.X	XX.X	XX.X
Maximum	XX	XX	XX	XX	XX	XX	XX

[a] The CPX-POM exposure expressed in days is defined as the number of days between the first dose taken date and the last dose taken date + 1 day.

[b] The CPX-POM exposure expressed in mg is defined as: dose per m² x Body Surface Area x CPX-POM exposure expressed in days.

Program: (Program name.sas) (run on: DDMMYYYY HH:MM)

Filename: (Specify file name.rtf)

Sponsor: CicloMed
Protocol: CPX-POM-001
Statistical Analysis Plan
(TFL shells):
Version 1.0 / 02FEB2018

Protocol: CPX-POM-001

--- DELIVERY TYPE ----

Page 1 of 2

Table 14.2.1 - Patients who have had at least one other post-baseline tumor assessment
(Efficacy Population)

	CPX-POM 30 mg/m ² N=1	CPX-POM [D2] mg/m ² N=X	CPX-POM [D3] mg/m ² N=X	CPX-POM [D4] mg/m ² N=X	CPX-POM [D5] mg/m ² N=X	CPX-POM [D6] mg/m ² N=X	CPX-POM [D7] mg/m ² N=X
At least one other post-baseline tumor assessment	XX (XX.X)	XX (XX.X)	XX (XX.X)	XX (XX.X)	XX (XX.X)	XX (XX.X)	XX (XX.X)

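### The Efficacy population requires a post-baseline tumor assessment that the protocol does not plan for patients who stop before the first scan, so they drop out of the response table instead of counting as not evaluable

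*SAP*

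**What the plan says.** The SAP as supplied consists of table and listing shells. The footnote to Table 14.1-2 defines the Efficacy population as patients with at least one dose who "had RECIST measurable disease at baseline and had at least one other post-baseline tumor assessment". Two tables use it: "Table 14.2.1 - Patients who have had at least one other post-baseline tumor assessment", and Table 14.2.2, which shows target, non-target and overall response by visit, each with a not-evaluable row. The protocol defines only a Safety Set and a Pharmacokinetic Set (Section 9.2), so this is the only efficacy set in the supplied documents.

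On the timing of scans, Protocol Section 8.1 has response assessments "repeated before the first study drug dose (Day 1) of every second cycle (i.e., at approximately 6-week intervals"). Footnote 8 to Table 1 has them "repeated at the end of every second cycle (i.e., at approximately 6-week intervals"). The first visit row of Table 14.2.2 is Cycle 2 Day 1.

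For patients who leave early, Section 7.2 asks staff to "make every effort to complete the full set of evaluations scheduled for the Follow-up/Early Termination visit". Table 1 marks neither a cancer evaluation nor CT/MRI at that visit or at Day 22. Section 8.1 adds one provision, limited to those whose disease is measurable: for anyone who "discontinues from the study after 6 weeks and before a disease response assessment is scheduled, an additional assessment may be performed", once the Sponsor has been consulted. Section 4.1 states "No follow-up after completion of the Follow-up Visit is planned", apart from monitoring of ongoing treatment-emergent adverse events.

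**The concern.** Preliminary anti-tumor activity is a secondary objective (Section 3), and Table 14.2.2 is the table that reports it. Entry to its population depends on having stayed in the study long enough to be scanned. The patients who fail that condition are those who die, progress clinically or stop for toxicity early, and they are unlikely to be responders. The exclusion therefore depends on outcome.

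The not-evaluable rows do not repair this. They can hold a patient whose post-baseline scan could not be evaluated, but not a patient who had no post-baseline scan. The first row of Table 14.2.1 does not reveal the loss either, because it counts the condition that defines its own population.

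**Working it through.** The plan gives no response rate, early-stopping rate or sample-size formula for response, so the check covers timing first and then the direction of the effect.

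**Inputs from the documents.** Cycle length 21 days with dosing on Days 1 to 5 (Section 6.1.4); Follow-up visit 28 ± 5 days after the last dose (Synopsis, Table 1); about 24 escalation patients (Section 9.1).

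**Timing**

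1. Two cycles: 2 × 21 = 42 days = 6 weeks, which agrees with the stated interval. The first scan on that schedule falls at about 42 + 1 = Day 43 (Cycle 3 Day 1).
2. In the shells the first scan is at Cycle 2 Day 1: 21 + 1 = Day 22.
3. A one-cycle patient has the last dose on Day 5. Follow-up is at 5 + 28 = Day 33, with a window from 5 + 23 = Day 28 to 5 + 33 = Day 38. This reproduces the Synopsis, which puts the visit 28 ± 5 days "after the last dose (i.e., approximately Day 33").
4. On the 6-week schedule, Day 38 comes before Day 43, so this patient finishes planned follow-up without a post-baseline scan. Section 4.5 nonetheless counts a patient who completes the first cycle as having completed the study.
5. On the shells' schedule the gap is narrower: it covers patients who stop in Cycle 1 and never reach the Cycle 2 Day 1 assessment.
6. The optional scan in Section 8.1 applies only after 6 weeks, so it does not close the gap on either schedule.

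**Effect on a percentage.** Let N be treated patients with measurable disease, m those with no post-baseline assessment and r responders, all of whom have been assessed. The proportion on the wider set is r/N. On the Efficacy count it is r/(N−m), so the ratio is N/(N−m). All values of N, m and r below are assumed.

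| N | r | m | r/N | r/(N−m) | Ratio |
|---|---|---|---|---|---|
| 24 | 2 | 2 | 8.3% | 2/22 = 9.1% | 1.09 |
| 24 | 2 | 4 | 8.3% | 2/20 = 10.0% | 1.20 |
| 24 | 2 | 6 | 8.3% | 2/18 = 11.1% | 1.33 |
| 24 | 2 | 10 | 8.3% | 2/14 = 14.3% | 1.71 |
| 12 | 2 | 3 | 16.7% | 2/9 = 22.2% | 1.33 |
| 6 (one dose) | 1 | 1 | 16.7% | 1/5 = 20.0% | 1.20 |
| 3 (one dose) | 1 | 1 | 33.3% | 1/2 = 50.0% | 1.50 |

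N = 24 is an upper illustration for the escalation cohorts, because measurable disease is an entry requirement only for expansion cohorts (Section 5.1, criterion 15).

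**Other denominators.** If percentages use patients assessed at the visit, the exclusion does not shift them. If they use all patients in the dose group, the response percentage does not shift, but m patients fall in no category: with 24 in the group and m = 4, the categories sum to at most 20/24 = 83.3%. With r = 0 the result is 0% in every case.

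**Scale.** The exact (Clopper-Pearson) 95% interval for 2/24 is 1.0% to 27.0%, and for 2/20 it is 1.2% to 31.7%. A shift from 8.3% to 10.0% is small against either.

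**The case against.** The strongest case on the other side is that a response-evaluable set is a defined, disclosed choice for a descriptive Phase 1 display. Table 14.1-2 prints the Efficacy count by dose as a share of enrolled patients. Table 14.1-1 gives reasons for discontinuation by cycle. The lesion and disposition listings cover all patients, so with about 24 patients a reader could largely count m. The shells have no best overall response or pooled response-rate row, so the pooled figures above concern a statistic they do not report, on assumed counts. All of this stands as a limit on the harm, but a listing does not correct the table that will be read.

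Four stronger readings are tempting, and the documents do not support them:

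- A reader might infer that Table 14.2.2 has no denominator. It has no percentage footnote, but neither do the adverse-event and disease-characteristics shells, which rely on the header N of the named population. The natural reading here is likewise the Efficacy count.
- A reader might infer that early leavers can never enter the set. Nothing bars an unscheduled scan, and one would bring the patient in. The point is only that none is planned.
- A reader might infer that every one-cycle patient is lost because Day 43 falls after Follow-up. That holds on the 6-week schedule, but the response and lesion shells use Cycle 2 Day 1.
- A reader might take the imaging row of Table 1 to mean that no on-study scans occur, since it marks Screening only. Footnote 8 and Section 8.1 govern on-study scans, and the cancer-evaluation row is also marked at Day 1.

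Finally, a footnote to Listing 16.2.8-5 refers to SAP text that is not in the supplied file. That text may already set the denominator and best-response rules.

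**Conclusion.** The point holds for the analysis population. Followed as written, and without unscheduled scans, the plan removes treated patients with measurable disease from the response display when they stop before the first scan, for reasons linked to outcome. It also leaves no row in which to show them. This is true whether the first scan is at Cycle 2 Day 1 or at about Day 43; the schedule changes only how many patients are affected.

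The direction is known when the Efficacy count is the denominator and there is at least one responder and at least one unassessed patient: a percentage that counts all N−m Efficacy patients is raised by N/(N−m). The size cannot be derived from the documents, because neither the number of early stoppers nor the number of responders is given. The endpoint is descriptive, no test depends on it, and the MTD is unaffected. The change is worth making before the tables are produced, but it does not threaten the primary objective. Confidence is medium, because the SAP text behind the shells was not available.

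**What to change.** Summarise response on all treated patients with measurable disease at baseline, and state that count as the denominator. Add a best overall response row with a written derivation. Show patients with no post-baseline assessment as not evaluable, count them as non-responders, and give the reason (for example death, toxicity, clinical progression, consent withdrawn, lost to follow-up). Keep the present Efficacy set as a supportive display. Move the first row of Table 14.2.1 to the wider set, where it becomes informative instead of being 100% by construction. Reconcile the timing of the first scan across Table 1 footnote 8, Section 8.1 and the first row of Table 14.2.2.

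The cost is edits to the shells and footnotes, plus one derivation rule and its programming; no extra scans or visits are needed. Reported rates may be slightly less favourable. If the SAP text outside the supplied file already sets these rules, repeating them in the shell footnotes is enough.
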